Patient Selection: 276 parents of Medicaid-insured children ages 2-12 years inclusive, seeking asthma care at Seattle Children’s or Mary Bridge Children’s emergency department who are the primary owners of a mobile phone with text messaging service.

Outcomes: Outcome data on parental self-efficacy and outcome expectations, adherence to asthma care treatment recommendations (e.g. primary care utilization), and child

asthma outcomes (e.g., ED visits, asthma morbidity) will be collected via structured telephone interviews at 3, 6, 12, 18, and 24 months post- enrollment.

Study Aims & Hypotheses

Aim 1: To improve urban, low-income children’s asthma-related health outcomes (primary outcome: reduced ED visits for asthma care, secondary outcome: lower morbidity) over 12 months.

Hypothesis 1a: Children of parents who receive T2B will make fewer ED visits for asthma care than those receiving standard ED asthma care alone.

Hypothesis 1b: Parents who receive T2B will report lower morbidity (i.e., days of impairment) than those receiving standard care.

Aim 2: To improve adherence to asthma care guidelines (primary care utilization for asthma care and improved parent asthma care self-management) over 12 months.

Hypothesis 2a: Parents who receive T2B will report increased primary care utilization (i.e., more frequent follow-up with their child’s PCP for routine asthma care) than those receiving standard care.

Hypothesis 2b: Parents who receive T2B will demonstrate greater knowledge of asthma self-management than those receiving standard care.

Hypothesis 2c: Primary care utilization and improved self-management will mediate the effect of T2B on children’s asthma-related health outcomes.

Aim 3: To improve parent cognitions (parental self-efficacy and outcome expectations) regarding partnering with their child’s PCP for asthma care over 12 months.

Hypothesis 3a: Parents who receive T2B will report greater self-efficacy in communicating with their child’s PCP about their child’s asthma care and greater outcome expectations for effective treatment and control of their child’s asthma symptoms than those receiving standard care.

Hypothesis 3b: Parental self-efficacy and outcome expectations will mediate the effect of T2B on adherence to asthma care guidelines.

Background and Study Rationale

Pediatric Asthma Epidemiology

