enhanced HC intervention to parents of children with other chronic conditions. In addition, the expedience of scaling up a text-message protocol means that our intervention can easily be adapted to reach a broader audience in a cost-effective manner when compared to ongoing face-to-face interventions. If efficacy is demonstrated, another next step will be to expand the program to other healthcare settings, such as primary care practices.

Study Design

We propose to conduct a RCT with low-income parents of children with physician-diagnosed asthma, ages 2-12 years inclusive, who are seen in the Seattle Children's or Mary Bridge Children's ED [for asthma care] to test the efficacy of our mHealth HC intervention, T2B, primarily for reducing ED/urgent care visits for asthma care. Each hypothesis will be tested by contrasting parents receiving T2B with parents receiving only standard ED-based care for their child's asthma, over 12 months.

Study Schedule

Data on child and parent outcomes will be collected in-person at enrollment and by telephone interviews at 3, 6, and 12 months post-enrollment. These telephone interviews will all be coordinated and conducted by the Seattle Children's study staff. Given the highly seasonal nature of asthma-related morbidity, the text message component of the intervention will continue for 12 months (3 months of biweekly educational interactive text messages; ongoing parent-initiated access to key messages and reminder text messages for PCP follow-up/medication refills/annual flu vaccines) allowing for the capture of individual variability in disease course. (Figure 3).

[figure not shown]

Figure 3

Study Population

The study population will be parents/guardians of Medicaid- insured patients seen in the Seattle Children’s or Mary Bridge Children’s ED for treatment of their asthma. These are patients whose asthma is not yet well controlled and who experience the greatest morbidity due to environmental and social factors and are thus the most resource-intensive group.

Inclusion criteria: Parents of Medicaid-insured children age 2 to 12 years inclusive with physician- diagnosed asthma for at least 12 months will be eligible. Older children/adolescents are excluded because they assume greater responsibility for asthma self-management, and their communication with providers becomes more independent over time. Parents must be

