Trained CRAs will conduct structured in-person interviews after participants have consented and before randomization. Follow-up interviews, lasting approximately 30 minutes, will be conducted by a trained CRA blinded to participants' randomization. In cases when no blinded CRA is available an unblinded CRA may complete the survey. Unblinded status will be documented for each survey conducted. Electronic medical record review will be conducted by trained study staff at the site where the participant was enrolled. Measures of asthma outcomes for this study are aligned with the recent recommendations of the Asthma Outcomes Groups for standardization of definitions and data collection methodologies for asthma research studies and clinical trials.^{75,76} All, but one of the following measures will be administered at each wave of data collection. The Asthma Self-Management Questionnaire will be administered at baseline and 12 months. (see appendix for Baseline Survey).

Distal Outcome Measures – Child Asthma Outcomes

ED visits for asthma care: Parents will report whether and how many times their child was taken to the emergency room because of asthma during the past 12 months using 2 questions administered in several national-scale surveys;⁷⁵ they will also indicate whether those visits included receipt of systemic corticosteroids.⁷⁶ We will validate a large portion of this data with EMR review because Seattle Children's is the primary ED utilized by young patients in the Seattle area and Mary Bridge Children's the primary ED utilized by young patients in the Tacoma area.

Asthma Morbidity: Asthma morbidity will be assessed by the questions used in the Inner City Asthma Consortium (ICAC)^{73, 74, 77, 78} and applied subsequently in numerous studies, including the study validating the IMPACT DC intervention.¹⁵ Morbidity will be measured as the number of days (or nights) of impairment in the prior 2 weeks.

Proximal Outcome Measures – Adherence to Treatment Recommendations

Primary Care Utilization: To maintain continuity in outcomes with the IMPACT DC RCT,¹⁵ we will ask parents to identify their child’s primary asthma health care provider, as well as their child’s primary care provider. A computed variable will indicate whether the named PCP is the child’s primary asthma health care provider. In addition, we will ask parents about frequency of PCP visits for asthma care at each telephone follow-up interview.

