COVER PAGE

Text2Breathe: Enhance Parent Communication to Reduce Pediatric Asthma Disparities (T2B)

NCT03032159

July 10, 2014

C.5. Statistical Analyses

C.5.a: Preliminary Descriptive Analysis of Data

We will summarize all baseline variables overall and by study arm to assess the balance achieved by randomization and to check assumptions such as normality and equality of variances. The distributions of continuous variables will be summarized using means, standard deviations, medians, and ranges. Categorical variables will be summarized using frequency distributions. Non-parametric tests (e.g., Wilcoxon rank-sum and Fisher's exact) will be used in subsequent analyses as needed. Cronbach alpha reliabilities will be estimated for 12 all standardized instruments to assess whether the instruments are as reliable in our target population as in the population on which the instruments were validated. Frequency of missing data for each outcome variable will be determined at each time point. Baseline characteristics of missing and non-missing respondents at the 3, 6, 12 and 24 month time points will be compared to assess for attrition bias. We will employ multiple imputation to account for missing data, if necessary.^{84, 85} We will examine counts of mobile interactions captured by Rip Road (e.g., number of messages received and sent by each participant; See section 5.1.d.) to assess engagement with the intervention, overall and by participant characteristics.

C.5.b: Analysis Plan for Addressing Specific Aims

In **Aim 1**, to assess the intervention effect on the primary and secondary distal outcomes (i.e., the number of ED visits for asthma care during the 12-month interval following randomization, and the number of days of impairment during the two weeks prior to the 12-month interview, respectively), we will utilize negative binomial regression, a generalization of Poisson regression which yields unbiased inference even if the outcome variable is over-dispersed (i.e., the variance exceeds the mean) to estimate incidence rate ratios (IRRs) and 95% confidence intervals (CIs) for count data. The single independent variable in each model will be study group, and the exponentiated form of its regression coefficient will reflect the relative difference between groups in the annual rate of ED visits or frequency of impaired days.

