In **Aim 3**, we will use linear regression models, as above, to evaluate the intervention effect on measures of self-efficacy and outcome expectations. We will then use path analysis to assess whether parental self-efficacy and outcome expectations (defined using the three validated instruments) mediate intervention effects on PCP follow-up rates and knowledge of self-management. Although the data collected at the 12-month time point will be used as our primary indicator of intervention effectiveness, we will also utilize data collected through the full 24-month follow-up period to evaluate sustainability of the hypothesized effects of the intervention in the same series of analyses. The above analyses estimate the impact of the intervention at observed levels of acceptance of the intervention and thus estimate the expected average effectiveness of the intervention if implemented in a similar population. We will also estimate the magnitude of the effect on each outcome under alternative levels of engagement in the intervention to provide a range of estimated effects based on greater and lesser levels of engagement. Moreover, we will examine potential moderating effects of race/ethnicity on the intervention effects.

C.5.c: Sample Size Estimate

All sample size and power analyses are based on a 2-tailed type 1 error of 5% in final analyses based on 12 month follow-up results. For the primary outcome under **Aim 1** (number of ED visits for asthma care during a 12-month interval), we calculated that a sample size of 125 per study group provides at least 90% power to detect a clinically important 35% reduction in the T2B group compared to the estimated average rate of 1.28 ED visits per year in the usual care group (based on 2012 ED records). For the primary outcome under **Aim 2** (number of PCP visits for asthma care during a 12-month interval), we calculated that a sample size of 120 participants per group provides 90% power to detect an increase to the recommended 3 annual visits in the T2B group over the observed rate of 1.8/year in the previous IMPACT DC sample.⁷ For the other outcomes under Aim 3 (self-efficacy and outcome expectation), a sample size of 85 per group provides 90% power to detect a 0.5 SD effect size difference between study groups. A feasible **analytic sample size of 110** ensures >80% power in all aforementioned analyses.

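### The Aim 1 morbidity test uses one two-week window at month 12, so the 3- and 6-month values of the same measure inform no between-arm estimate for the year

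*SAP*

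**What the plan says.** **Aim.** The Protocol (Study Aims & Hypotheses, Aim 1) lists morbidity as "secondary outcome: lower morbidity) over 12 months".

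**Measure.** Protocol, Data Collection: "Morbidity will be measured as the number of days (or nights) of impairment in the prior 2 weeks". The same section says "All, but one of the following measures will be administered at each wave of data collection"; the one exception is the self-management questionnaire. Study Schedule places follow-up "by telephone interviews at 3, 6, and 12 months post-enrollment". Impairment days are therefore available at baseline and at three follow-up waves within the year.

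**Test.** SAP C.5.b, Aim 1, defines the morbidity endpoint as "the number of days of impairment during the two weeks prior to the 12-month interview" and analyses it by negative binomial regression. "The single independent variable in each model will be study group". Neither the 3- and 6-month values nor baseline impairment enter this model.

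**Other uses of the interim data.** The Aim 2 part of C.5.b includes impairment days among the outcomes of its mediation analyses: path models fitted wave by wave, and latent growth models across waves. The Aim 3 part adds that "the data collected at the 12-month time point will be used as our primary indicator of intervention effectiveness", with later data used to look at sustainability.

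**Missing data.** C.5.a allows multiple imputation if it is judged necessary, without an imputation model. C.5.c plans for 80% retention at 12 months.

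**The concern.** The aim refers to a year, and the test looks at 14 of 365 days (3.8%). The ED-visit outcome defined in the same SAP sentence is counted over the whole 12 months. Three features of this trial make the difference matter.

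- **Season.** The Protocol's Study Schedule justifies a 12-month text programme with "Given the highly seasonal nature of asthma-related morbidity". The month-12 interview, with a window of one month either side, falls about a year after the enrolling ED visit. Each child is therefore observed in roughly the season of enrolment; months 3 and 6 sample other seasons.
- **Time course.** Programme-initiated education runs for the first 3 months, followed by on-demand messages and reminders. In the predecessor face-to-face trial described in the Protocol, the effects on healthcare use were seen at 2 months and not sustained at 6. An early effect on morbidity is plausible, and a test at month 12 alone could miss it.
- **Missing data.** A family that answers at 3 and 6 months but not at 12 is left out of the Aim 1 model unless its value is imputed.

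At stake are precision on a secondary outcome and the chance to say anything between arms about the year as a whole.

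**Working it through.** **Inputs from the documents.** 110 analysed per group, two-sided 5% error, 80% retention at 12 months (SAP C.5.c); follow-up waves at 3, 6 and 12 months (Protocol, Study Schedule); a two-week recall window (Protocol, Data Collection).

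**Inputs that are assumed.** The documents give no mean, dispersion or between-wave correlation for impairment days, so a negative binomial calculation is not possible. I use a normal approximation in SD units, a common correlation ρ of 0.3 to 0.7 between waves, equal variance at each wave and complete data.

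**The plan's own figures.**
- Enrolment: 110 / 0.80 = 137.5, rounded up to 138 per group. This matches the SAP.
- Scale outcomes: n = 2 × (1.960 + 1.282)² / 0.5² = 84.1, rounded up to 85 per group for 90% power at 0.5 SD. This matches the SAP.
- The SAP gives no power figure for morbidity.

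**Single window at month 12.** Detectable difference with 80% power at 110 per group: (1.960 + 0.842) × √(2/110) = 0.378 SD.

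**Average of three waves, constant effect.** The variance relative to one wave is (1 + 2ρ)/3.

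| ρ | Variance ratio | Equivalent single-window n per group (110 / ratio) | Detectable difference, 80% power | Power at 0.378 SD |
|---|---|---|---|---|
| 0.3 | 0.533 | 206 | 0.276 SD | 97% |
| 0.5 | 0.667 | 165 | 0.308 SD | 93% |
| 0.7 | 0.800 | 138 | 0.338 SD | 88% |

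The gain in equivalent families runs from 1/0.800 − 1 = 25% to 1/0.533 − 1 = 88%. The standard error is smaller by 1 − √0.800 = 11% to 1 − √0.533 = 27%.

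**Effect not constant.** Power to show benefit, with 0.378 SD at the waves where the effect is present and nil elsewhere:

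| Effect present at | Mean effect over three waves | Month-12 test | Three-wave average (ρ = 0.3 to 0.7) |
|---|---|---|---|
| Months 3 and 6 only | 0.252 SD | 2.5% (chance) | 73% to 55% |
| Month 12 only | 0.126 SD | 80% | 25% to 18% |

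For example, at ρ = 0.3 the standard error of the average is √(2 × 0.533/110) = 0.0985. For an early-only effect, 0.252/0.0985 − 1.960 = 0.60, which gives 73%.

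**Coverage.** Three windows cover 42 of 365 days (11.5%), against 14 (3.8%) for one.

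**The case against.** The strongest defence is that month 12 is a deliberate, pre-specified target. The SAP declares it the primary indicator and bases power on it. The 12-month phrase is attached to all three aims. Aim 2 includes self-management, whose questionnaire is given only at baseline and month 12, so there the phrase can mean only the follow-up horizon. Read that way, Hypothesis 1b needs no more than the words at 12 months. This stands: the endpoint is legitimate, and averaging the waves estimates something different. The average also leaves the stretch between months 6 and 12 unobserved.

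Three stronger readings are tempting, and the documents do not support them.

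- A reader might infer that the 3- and 6-month values are thrown away. They are not: the Aim 2 path and growth models use them. Those models address mediation, however, and specify no comparison of the arms on morbidity over the year.
- A reader might infer that a family missing month 12 can contribute nothing. Multiple imputation is allowed, and earlier waves could inform it, although the SAP does not say that they would.
- A reader might infer seasonal bias. Randomisation prevents it. Enrolment over 24 months with a planned 6 to 18 families per month also spreads the month-12 windows over the calendar at group level. What remains is that each child is seen in roughly one season.

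Finally, the gain in precision is conditional. Equal variance is doubtful for a seasonal outcome, and a late-building effect reverses the advantage.

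**Conclusion.** The point holds as one of lost information on a secondary outcome, and as the absence of any planned between-arm estimate of morbidity across the year. It does not show that the month-12 analysis is biased or invalid.

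The size of the loss rests wholly on the assumptions listed in the working, including a constant effect. It is a guide to scale; it says nothing about which time course will occur. Because the two contrasts fail under opposite time courses, neither can safely stand in for the other. The matter is minor in severity and cheap to put right.

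**What to change.** In SAP C.5.b, Aim 1, replace the single-window morbidity model with one repeated-measures log-mean count model (GEE or mixed, with robust variance) for impairment days at 3, 6 and 12 months. Include arm, wave, arm-by-wave and baseline impairment.

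From that model:
- keep the month-12 contrast as the declared result, in line with the SAP's choice of primary time point;
- report the average of the three waves beside it, with the weights stated in advance (for example, equal weights on the log scale), as the estimate for the 12-month aim;
- show both whatever their results.

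State how the model treats families with some waves missing and whether interim values enter any imputation, so that those who miss month 12 still contribute. Reword Hypothesis 1b to say which contrast it refers to.

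The cost is SAP wording and a little more analysis; no new data are needed. The downside is that the average can understate an effect that builds late, which is why it accompanies the month-12 contrast and does not replace it.

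### Impairment days cannot exceed 14, so the planned negative binomial standard error can be wrong in either direction; a robust variance should be pre-specified

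*SAP*

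**What the plan says.** SAP C.5.b, Aim 1, covers two outcomes with one model: ED visits over 12 months (primary) and, as the secondary outcome, "the number of days of impairment during the two weeks prior to the 12-month interview". The protocol (Data Collection, Asthma Morbidity) defines the second in the same window: "Morbidity will be measured as the number of days (or nights) of impairment in the prior 2 weeks".

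Both are analysed by negative binomial regression, justified as "a generalization of Poisson regression which yields unbiased inference even if the outcome variable is over-dispersed". On covariates the SAP says: "The single independent variable in each model will be study group". Incidence rate ratios with 95% confidence intervals are to be reported.

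The SAP does not say whether standard errors are model-based or robust, and does not mention the upper limit that a two-week window implies. C.5.a allows non-parametric tests where needed, without a trigger. C.5.c gives no mean, spread, effect size or power for impairment days.

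**The concern.** The negative binomial model sets variance = m + k·m², where m is the mean and k the dispersion. That form has no ceiling. A count of days in a fortnight stops at 14, so its variance can follow another pattern. Allowing for over-dispersion is not the same as allowing for a ceiling, and the SAP's assurance of unbiased inference does not carry over from ED visits to this outcome.

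The single k is fitted by maximum likelihood to the whole shape of the data, including the zeros. If the shape is not negative binomial, the fitted k need not reproduce the actual variance, and a model-based standard error inherits the mismatch. At stake are the interval and p-value for the named secondary outcome (Hypothesis 1b). They could hide a real effect or suggest one that is absent.

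**Working it through.** **1. The plan's own figures.** None exists for impairment days. The neighbouring ones reproduce:
- Enrolment: 110/0.80 = 137.5, so 138 per group and 276 in total. The analytic 110 is therefore per group and is used below.
- Aim 3: 2 × (1.960 + 1.282)²/0.5² = 84.1, so 85 per group.
- ED visits: the SAP states that "a sample size of 125 per study group provides at least 90% power to detect a clinically important 35% reduction", from an "estimated average rate of 1.28 ED visits per year in the usual care group". With no over-dispersion, (1.960 + 1.282)² × (1/1.28 + 1/0.832)/(ln 0.65)² gives 113 per group, so 125 is consistent with at least 90%.

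The SAP's claim of more than 80% power at 110 refers to ED visits, PCP visits and the Aim 3 scales.

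**2. What is and is not affected.** With study group as the only term, the fitted means equal the arm means, so the rate ratio is the ratio of means whatever the variance. With n per arm and sums over the two arms:
- model-based variance of the log ratio = Σ(1/m + k)/n
- robust variance = Σ(s²/m²)/n, where s² is the arm's sample variance

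They agree only if s² = m + k·m².

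**3. A shape where the model error is too wide** (assumed: beta-binomial, 14 days, mean 3.5, within-child correlation 0.5).
- Variance = 14 × 0.25 × 0.75 × (1 + 13 × 0.5) = 19.69.
- k that matches this variance = (19.69 − 3.5)/3.5² = 1.32.
- True SE under no effect = √(2 × 19.69/(110 × 3.5²)) = 0.171.
- Simulated ratio of model SE to true SE = 1.27, so model SE ≈ 0.217. The fitted k is then about 0.217² × 110/2 − 1/3.5 = 2.3, well above 1.32.
- Type I error 1.3% model-based, 5.1% robust. Power for about a 35% reduction: 39% against 58%.

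**4. A shape where it is too narrow** (assumed: 5% of children averaging 13 days, the rest averaging about 0.7; overall mean 1.31, variance 8.1).
- k that matches the variance = (8.1 − 1.31)/1.31² = 3.96; average fitted k = 2.35.
- Model SE = √(2 × (1/1.31 + 2.35)/110) = 0.238; true SE = √(2 × 8.1/(110 × 1.31²)) = 0.293. Simulation gave a ratio of 0.80.
- Type I error 11.7% model-based, 6.1% robust. Rejection rate under the alternative: 40% against 26%.

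**5. The direction turns on the shape.** Keeping the shape in step 4 and changing only the share of children near 14 days:

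| Share near 14 | Model SE / true SE | Type I, model | Type I, robust |
|---|---|---|---|
| 5% | 0.80 | 11.7% | 6.1% |
| 10% | 0.91 | 8.0% | 5.7% |
| 20% | 1.14 | 3.0% | 4.7% |

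**6. Range over assumed shapes, 110 per group.**
- Beta-binomial, means 2-7 days: ratio about 1.02-1.40; model-based type I error about 0.5-4%; power for a 35% reduction lower by about 0-26 points. At mean 4 it is 60% against 72% with correlation 0.4, and 35% against 60% with 0.6. At mean 3 and correlation 0.2 it is only 78% against 82%.
- A wider set of bounded shapes, adding zero-inflated and capped counts: ratio 0.99-1.64, power gap up to 41 points.
- Mostly low counts with 2-10% of children at or near 14: ratio 0.80-0.94; model-based type I error 6.7-11.9%, robust 5.3-6.4%.
- Negative binomial capped at 14, mean 2.5, k = 0.5: no difference (power 89% both ways).
- Robust type I error was about 4-6% in these settings. In one very skewed low-mean mixture it reached 7.7%, where the model-based figure was 14.1%.

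**The case against.** The strongest objection is that nothing in the documents fixes the shape of this outcome, so neither the direction nor the size of any error is known. That stands. A reader might infer that the ceiling always makes model-based errors too wide, so that the plan loses power which a robust variance restores at no cost. The documents do not support this. Steps 4 and 5 show the opposite sign under equally possible shapes, and there a robust variance lowers the rejection rate. No power is planned for impairment days, so there is no baseline to lose from. The protocol (Study Population) describes children whose asthma is not yet well controlled, which makes higher means plausible at entry but does not settle the picture at 12 months.

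It is also fair that the SAP never says the errors are model-based. That is the usual software default, not a stated choice; equally, no robust option is stated.

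The non-parametric fallback in C.5.a helps little: it has no trigger, and a rank test gives no rate ratio or interval. Finally, this is a secondary outcome, and the primary ED-visit analysis is outside this point.

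**Conclusion.** The point holds as one about validity. For a 0-14 outcome the SAP's assurance of unbiased inference is too strong: the ratio of means is sound, but a model-based interval and p-value can be conservative, anti-conservative or correct, depending on a shape that cannot be known beforehand. The ranges in step 6 illustrate this and do not predict what the trial will show.

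The conclusion assumes that the errors would be model-based by default, that 110 per group are analysed, and that the outcome is a single count with a maximum of 14. That maximum is implied by the two-week window but not printed. This is a cheap improvement rather than a serious flaw, held with moderate confidence.

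**What to change.** In SAP C.5.b, Aim 1, for impairment days:
- keep the log link and the ratio of means, and pre-specify robust (sandwich) standard errors, or use a quasi-binomial or beta-binomial model with denominator 14;
- limit the sentence on unbiased inference to ED visits;
- state that the outcome ranges from 0 to 14.

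With sandwich errors the cost is a line of text and a software option; the effect measure and sample size do not change. A binomial-type model would need a stated way to report the ratio of means. The statistical downside is small: type I error slightly above 5% (to about 6%, rarely more) in very skewed data, and a lower rejection rate where the model-based error would have been too narrow. Fixing the estimator now also avoids choosing it after the data are seen.
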